## **INTRAOPERATIVE RADIOGRAPHIC DETECTION OF RETAINED SURGICAL SPONGES**

### **OBJECTIVE**

The aim of this prospective study is determine the efficacy of intraoperative x-ray to rule out retained surgical sponges.

### **BACKGROUND**

Retained surgical sponges can be result in serious medical morbidities such as infection, pain, abscess and contribute to medicolegal problems. In a retrospective control study with nearly two hundred thousand surgeries, the retained foreign object rate was found approximately 1/5500 [Cima 2008]. Sponges were the most common items left behind [Lincourt 2007]. Even though there are strict protocols to account for every surgical sponge used during a procedure, human error is not zero. When a retained surgical sponge is suspected, intraoperative x-ray images can be obtained to rule out a foreign body [Turgut 2018]. One radiographic image of the surgical field is most commonly preferred. However, a retained surgical sponge may not appear on intraoperative x-rays. The aim of this study is to determine how sensitive and specific x-rays are for detecting retained surgical sponges. Another aim of this study is determine if two views of the surgical field improve detection of retained sponges and may decrease false negative rates.

### **METHODS**

#### **Study Design**

This is a prospective, randomized study with two cohorts: one experimental and one control. Anteroposterior (AP) and lateral (LAT) radiographs are routinely obtained as standard of care during spine surgery to confirm proper implant placement. These images will be used in this study. In one-half of the study subjects, a surgical sponge will be intentionally placed in the surgical field prior to imaging. Postoperatively, three spine surgeons (Fellows of Twin Cities Spine Center) who did not participate in the surgery will assess the images for the presence or absence of a retained surgical sponge.

#### **Sample Size**

Our hypothesis for statistical analysis is that there will be 90% sensitivity/specificity [Revesz 1983]. For a 95% confidence interval with  $p=0.05$ , a sample size of  $n=146$  is estimated [Jones 2003].

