### **Randomization**

Randomization will be performed prior to surgery using sealed envelopes. One hundred forty six (146) envelopes will be sequentially numbered and 146 chits with either the number “1 (retained sponge, n=73) or the number “2” (no retained sponge, n=73) will be prepared. Chits will be drawn at random and sequentially placed in the envelopes, which will be sealed. For each consented subject, when surgery is scheduled, an envelope will be opened and the surgery worksheet annotated, as appropriate.

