## Methods

For subjects in study group 1, the following will happen:

- OR staff will count surgical sponges, as is routine.
- AP and Lateral radiographic images will be taken of the surgical field. (This is Standard of Care, because radiographic images are taken for all patients to confirm correct placement of the instrumentation.
- Just prior to imaging, the surgeon will purposely place a sponge in the wound. He will state this to the circulating nurse and scrub tech.
- After imaging, the surgeon will remove the sponge. He will state that he has removed the sponge; the scrub tech will confirm that the sponge has been removed; the circulating nurse will note this in your chart.
- OR staff will re-count surgical sponges to be certain none are left in the wound.

For subjects in study group 2, the following will happen:

- Two radiographs will be taken of the spine (AP and Lateral views) to verify that the instrumentation is placed properly.
- OR staff will re-count surgical sponges to be certain none are left in the wound.

For all subjects:

Images will be stored on Allina's medical record system. Three investigators (TCSC Fellows, TBD) not participating in the surgery will independently view the images and note if a retained sponge is visible on either image or both.

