## Statistical Methods

This study will quantify the relative specificity, sensitivity, positive and negative predictive values, and accuracy of 1) an AP image alone, 2) a LAT image alone, and 3) AP and LAT images together. The results will be analyzed to determine effects of demographic and surgical variables. The McNemar test and generalized linear mixed models will be used as statistical tools [Hellbach 2018].

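### The sample size of 146 does not follow from its stated inputs (90%, 95% interval, an undefined p=0.05); the precision that 73 patients per measure give should be stated

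*Combined protocol and SAP*

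**What the plan says.** The protocol's Sample Size section is two sentences long. The first gives the planning value: "Our hypothesis for statistical analysis is that there will be 90% sensitivity/specificity". The second gives the result: "For a 95% confidence interval with $p=0.05$ , a sample size of $n=146$ is estimated", with a citation to a general paper on sample size. The section gives no half-width, null value, power, formula or loss allowance, and does not say whether 146 is a total or a number per measure.

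Other sections settle that last question. Under Study Design, "In one-half of the study subjects, a surgical sponge will be intentionally placed in the surgical field prior to imaging". The Randomization section prepares 146 envelopes, 73 for each group. Sensitivity therefore rests on 73 patients and specificity on the other 73.

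Under Methods, three surgeons "not participating in the surgery will independently view the images". Statistical Methods plans sensitivity, specificity, predictive values and accuracy for "1) an AP image alone, 2) a LAT image alone, and 3) AP and LAT images together".

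**The concern.** A precision-based sample size needs an expected proportion, a confidence level and a target width. The first two are stated. The third is either missing or is what p=0.05 was meant to convey, and the text does not say which. Different readings imply different planned precision, so a reader cannot tell what the trial was sized to deliver, or whether the size rests on 90% or on 95%.

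This matters because the stated aim is to "determine the efficacy of intraoperative x-ray to rule out retained surgical sponges". For that use the lower confidence limit of sensitivity carries much of the weight, since it bounds how many sponges could be missed. A reader who takes p=0.05 to mean ±5 points for each measure would expect more precision than 73 patients give for one reader.

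**Working it through.** **Inputs.** Proportion 0.90 and 95% confidence, so z = 1.96 (Sample Size). The value 0.05 has no stated meaning (Sample Size). There are 73 patients with and 73 without a sponge (Randomization), and three readers (Methods). Between-reader correlation and reader-to-reader variation are not given.

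**Formula.** For a single proportion P with half-width d: n = z² × P × (1 − P) / d².

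**A route that reproduces 146 exactly.** Use 0.05 both as the proportion (0.95 gives the same result) and as the half-width:
- 1.96² × 0.05 × 0.95 / 0.05² = 72.99, so 73 per group and 2 × 73 = 146.
- This matches the 73/73 split, but it replaces the stated 90%.

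**Readings that keep the 90%.**
- 0.05 as significance level: it repeats the 95% confidence level. No width, null value or power remains, so no n can be calculated.
- 0.05 as half-width, per measure: 1.96² × 0.9 × 0.1 / 0.05² = 138.3, so 139 for sensitivity and 139 for specificity, 278 in total. Requiring a Wilson half-width of 0.05 gives 141 per measure, 282 in total.
- 0.05 as half-width, over all patients: 1.96 × √(0.09/146) = 0.0487, about ±4.9 points. This applies only to a proportion that uses every patient. Accuracy is one: if sensitivity and specificity are both 90%, so is accuracy.

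**Other routes to 146, each with an unstated element.**
- A Wilson half-width of 0.07 at 90% needs 73 per group, 146 in total.
- 139 plus 5% is 139 × 1.05 = 145.95. This treats 146 as the number for one measure.

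**What 73 patients per measure give, one reader and one image set.**
- Wald at 90%: 1.96 × √(0.09/73) = 0.0688, about ±6.9 points.
- Wilson limits are [P + z²/2n ± z√(P(1 − P)/n + z²/4n²)] / (1 + z²/n). With P = 0.90 and n = 73 they are 81.0% and 95.0%, that is 9 points below and 5 above.
- Exactly 90% of 73 is 65.7, which cannot be observed. The nearest counts give 79.8% to 94.3% (65/73 = 89.0%) and 81.5% to 95.3% (66/73 = 90.4%).

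**Pooled over three readers.** There are 3 × 73 = 219 reads per group. Allowing only for correlation between reads of the same patient, the effective n is 219 / (1 + 2 × ICC):

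| Assumed ICC | Effective n | 95% Wilson at 90% |
|---|---|---|
| 0 | 219 | 85.3% to 93.3% |
| 0.5 | 109.5 | 83.0% to 94.3% |
| 1 | 73 | 81.0% to 95.0% |

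If the three surgeons stand for readers in general, differences in accuracy between readers add variance. With an assumed ICC of 0.5 and an assumed reader standard deviation of 5 points, 1.96 × √(0.09/109.5 + 0.05²/3) = 0.080, about ±8.0 points. That is wider than the ±6.9 for a single reader taken alone.

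**The case against.** The strongest reply is that nothing has been miscalculated. The total agrees with the allocation, several ordinary routes reach 146, and one input simply lacks a definition. That largely stands: it would be wrong to say that no reading gives 146. What can be said is that every route found to 146 for sensitivity or specificity adds or replaces an input.

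A second reply is that 146 suits accuracy, which Statistical Methods lists among the measures. The ±4.9 points for that measure is correct. But the Sample Size section names sensitivity and specificity, not accuracy, so this does not settle what was intended.

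A third is that the cited paper may explain p. It was not available for this review, so that cannot be excluded. The protocol should still state its own inputs.

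A fourth is that no section makes one reader and one image set the unit of inference, and mixed models are planned. This is fair. It is why the interval has to be labelled per reader and image set, and why no claim is made that pooling must narrow it.

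Two stronger readings are tempting. One is that the trial is too small, 146 against 278. The documents do not support this, because the comparison holds only if ±5 points per measure was the target, and no target is stated. The other is that the sponsor used 5% or 95% by mistake. The exact match at 72.99 is suggestive, but other routes also give 146, so this remains an inference.

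**Conclusion.** The point holds as a defect in the stated basis for the sample size. For sensitivity and specificity, 146 does not follow from 90%, a 95% interval and p=0.05 as written, and the intended route is unknown.

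The plan also does not report the precision it will deliver: about 81% to 95% for each measure at an observed 90%. At the lower limit, up to 19% of sponges missed would be compatible with the planned result. These figures assume the Wilson method, 73 evaluable patients per measure, and one reader with one image set.

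Neither a need for more patients nor an invalid analysis has been shown. The correction should be made, but it does not call the design into question.

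**What to change.** Keep 146. Ask the sponsor to say what p=0.05 means and to reconcile it with the 90%; it should not be deleted before its meaning is known. Then restate the Sample Size section along these lines:

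> 73 patients with and 73 without a sponge give, for sensitivity and for specificity separately, per reader and image set, a 95% interval of about 81% to 95% (Wilson) if the observed value is 90%. The precision of an estimate over three readers depends on between-reader correlation and reader-to-reader variation.

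Give the two limits and not a single ± figure, because the interval is not symmetric about 90%. If another interval method is preferred, name it and quote its limits. If ±5 points per measure was intended, state that 73 per measure does not provide it per reader.

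The cost is wording only, with no change to enrolment, allocation or analysis. The stated precision will look less favourable, and the new text describes what 146 delivers without by itself justifying that number.

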### **Subject Consent**

The PI will identify a potential subject based upon the recommended surgical treatment. Preoperatively on the day of surgery, the PI will explain the study to the patient and ask if he/she would be interested in participating. If the patient is interested in participating, TCSC research staff will consent the patient. Consenting will occur privately in the Preoperative Care Center (POCC).

### **Inclusion Criteria**

- Patients undergoing open posterior instrumented lumbar spine surgery.
- Read and understand English.

### **Exclusion Criteria**

- Pregnancy.
- Patients who do not consent to research.
- Patients less than 18 years old at the time of consent.
- Do not read and understand English.

### **Blinding**

This will be a semi-blinded trial. Investigators performing the surgery will know whether or not a sponge is present but the investigators reviewing the images will not. Subjects will not be told which study group they are in.

### **Randomization**

Randomization will be performed prior to surgery using sealed envelopes. One hundred forty six (146) envelopes will be sequentially numbered and 146 chits with either the number “1 (retained sponge, n=73) or the number “2” (no retained sponge, n=73) will be prepared. Chits will be drawn at random and sequentially placed in the envelopes, which will be sealed. For each consented subject, when surgery is scheduled, an envelope will be opened and the surgery worksheet annotated, as appropriate.

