## **STUDY OVERSIGHT**

The protocol, informed consent document and relevant supporting information will be submitted to the IRB for review and must be approved before the study is initiated. This study will be conducted in accordance with the ethical principles that have their origin in the Declaration of Helsinki and that are consistent with Good Clinical Practice and applicable regulatory requirements. The study will be conducted in accordance with the regulations of the United States Food and Drug Administration (FDA) as described in 21 CFR 50 and 56 [add 312 for IND studies or 812 for device studies], applicable laws and the IRB requirements. A protocol change intended to eliminate an apparent immediate hazard to subjects may be implemented immediately provided the IRB is notified within 10 working days.

It will be the responsibility of the investigator to provide each subject with full and adequate verbal and written information using the IRB-approved informed consent document, including the objective and procedures of the study and the possible risks involved before inclusion in the study. Informed consent will be obtained prior to performing any study-related procedures, including screening and changes in medications including any washout of medications. A copy of the signed informed consent will be given to the study subject.

Study data will be made available for monitoring, auditing, IRB review and regulatory inspection by providing direct access to study related source data. The study may be prematurely closed for administrative reasons by the Principal Investigator (for example, lack of enrollment, lack of adequate research staffing, lack of adequate funding). The study

may be prematurely by the safety monitors based on study progress or adverse events.

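### Could the randomization envelope be opened before the patient has consented?

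*Combined protocol and SAP*

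**What the plan says.** Randomization gives an outer limit, "Randomization will be performed prior to surgery using sealed envelopes", and then the working instruction: "For each consented subject, when surgery is scheduled, an envelope will be opened and the surgery worksheet annotated, as appropriate". It describes 146 sequentially numbered, sealed envelopes, filled by drawing chits at random, with 73 for the sponge group and 73 for the no-sponge group.

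Subject Consent sets the day: "Preoperatively on the day of surgery, the PI will explain the study to the patient and ask if he/she would be interested in participating". Research staff then take consent in the preoperative area. The PI has already identified the patient as a candidate from the surgical treatment recommended.

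Study Oversight states the general rule: "Informed consent will be obtained prior to performing any study-related procedures". Exclusion Criteria exclude patients who do not consent to research.

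No section says who opens the envelope, or describes a log of openings.

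**The concern.** An operation is normally booked before the patient arrives for it. Under Subject Consent, nobody has consented at booking. Taken literally, the Randomization sentence then asks for two things that cannot both be true at one moment: a consented subject, and surgery only now being scheduled.

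If staff resolved this by opening the envelope at booking, the group would be on the surgery worksheet before the PI approached the patient. Nothing says the PI would not see it. The PI could then, knowingly or not, approach some patients more readily for one group than for the other.

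In this design that would matter. Sensitivity comes only from the sponge arm and specificity only from the control arm, so selective enrolment could make the two rest on different kinds of patient, for example in weight or number of instrumented levels. Blinding the three image readers would not help, because the selection happens before the images exist. Envelopes opened for patients who later declined would also be used up, and exactly as many are prepared as subjects are planned.

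Two things are outside the concern. The surgeon must know the group at imaging, and the Blinding section says so. The comparison of AP, LAT and both views is made within each patient, so case mix does not confound it.

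**Working it through.** The question is one of order, so the main check is textual.

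| Section | What it fixes | Consent before opening? |
|---|---|---|
| Subject Consent | Study explained and consent taken on the day of surgery | Sets the earliest time a consented subject can exist |
| Randomization, working instruction | Opening applies to consented subjects | Yes, explicitly |
| Randomization, scheduling phrase | A time marker | Fits if it means the operation listed for that day; does not fit if it means booking |
| Randomization, outer limit | Before surgery | Fits either reading |
| Study Oversight | Consent before any study-related procedure | Yes, as a general rule |
| Exclusion Criteria | Non-consenting patients are excluded | Yes, by implication |

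One sequence satisfies every row: candidate identified, study explained, consent signed, envelope opened and worksheet annotated, surgery. Under the booking reading the instruction authorises no opening at all, because no consented subject exists yet. That reading gives an instruction that cannot be carried out; it does not give permission to randomize before consent.

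The allocation is internally consistent: 73 + 73 = 146.

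The figures that might suggest a large effect are these, taking the 90% in Sample Size ("Our hypothesis for statistical analysis is that there will be 90% sensitivity/specificity") and 73 subjects per arm:

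- Expected misses per reader: 73 × 0.10 = 7.3.
- Shift from one subject: 1/73 = 1.37 percentage points.
- Shift from five subjects: 5/73 = 6.85 points.
- 95% half-width: 1.96 × √(0.90 × 0.10/73) = 0.0688, or 6.9 points.

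So five subjects moved from missed to detected would equal about the whole half-width. The arithmetic is right, but it applies to five subjects altered for any reason and says nothing about envelope timing. Five fewer misses out of 7.3 is 5/7.3 = 68% of all misses, taking sensitivity from 90% to (65.7 + 5)/73 = 96.8%. To bring that about by selection, the PI would have to foresee before surgery whose sponge would go unseen on film. Nothing in the documents suggests this is possible.

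The cost of wasted envelopes can be bounded (both losses are assumptions):

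- 1 lost per arm: 1.96 × √(0.09/72) = 0.0693.
- 5 lost per arm: 1.96 × √(0.09/68) = 0.0713.

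Against 0.0688, these are changes of 0.05 and 0.25 percentage points.

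**The case for a change.** The strongest case for acting is practical. The scheduling phrase is the only statement of when the envelope is opened, other than that it happens before surgery, and busy staff may follow the phrase and not the logic around it. The text does not name the person who opens the envelope, does not say outright that the next number is taken, and describes no log. Allocation concealment is cheap to protect and cannot be restored once lost, so a clearer sentence would cost almost nothing.

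Part of this stands. The phrase is poorly chosen, and the roles are unstated. But the harm requires staff to disregard both the word consented in the very sentence they are following and the consent rule in Study Oversight. That would be a deviation from the plan. Once consent comes first, the worry about the PI seeing the worksheet also goes: the approach is over, and the group was sealed while it took place. The unstated details are ones a trial team fills in as routine, and numbering the envelopes in sequence already implies their use in sequence.

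A stronger measure would be to open the envelope in the operating room. It would conflict with the statement that randomization precedes surgery. It would also call for a further edit to the group steps under Methods, where the routine sponge count ("OR staff will count surgical sponges, as is routine") is listed for group 1 only. With consent already first, it has no demonstrated gain.

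**Conclusion.** No change to the plan follows. The time phrase in Randomization is a clerical looseness: read as booking, it does not fit day-of-surgery consent. The order that matters for concealment is nevertheless settled, because Randomization limits opening to consented subjects and Study Oversight requires consent first. Followed as written, the plan does not reveal the group before the patient is approached, so the route to selective enrolment is closed.

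The effect on the planned results is nil: the 146 subjects, the 73 per arm, the accuracy estimates and the within-patient view comparisons all stay as they are. The size of any bias from departing from the stated order cannot be derived from the documents, and the five-subject figure is not an estimate of it. The precision cost of wasted envelopes is at most about a quarter of a percentage point in half-width under the assumed loss of 5 per arm.

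The conclusion rests on staff applying the consent condition as written, and on the envelopes staying sealed until then, which the plan provides for. The derivation of 146 under Sample Size was not needed here and is not judged.

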### **Data Collection**

Demographic information will include sex, age, height, and weight. Surgical information will

include the number of levels decompressed and instrumented, type and configuration of instrumentation, use of bone graft and/or biologics, estimated blood loss, and length of surgery. Radiographic images will include AP and LAT views of the surgical field prior to closing.

## Methods

For subjects in study group 1, the following will happen:

- OR staff will count surgical sponges, as is routine.
- AP and Lateral radiographic images will be taken of the surgical field. (This is Standard of Care, because radiographic images are taken for all patients to confirm correct placement of the instrumentation.
- Just prior to imaging, the surgeon will purposely place a sponge in the wound. He will state this to the circulating nurse and scrub tech.
- After imaging, the surgeon will remove the sponge. He will state that he has removed the sponge; the scrub tech will confirm that the sponge has been removed; the circulating nurse will note this in your chart.
- OR staff will re-count surgical sponges to be certain none are left in the wound.

For subjects in study group 2, the following will happen:

- Two radiographs will be taken of the spine (AP and Lateral views) to verify that the instrumentation is placed properly.
- OR staff will re-count surgical sponges to be certain none are left in the wound.

For all subjects:

Images will be stored on Allina's medical record system. Three investigators (TCSC Fellows, TBD) not participating in the surgery will independently view the images and note if a retained sponge is visible on either image or both.

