## **CONFIDENTIALITY**

Data will be stored on TCSC computers, which are linked by Allina Health servers. No data will be physically removed from TCSC. The United States Food and Drug Administration may inspect all records related to the study. The IRB and/or other regulatory authorities (for example, the United States Food and Drug Administration) will have access to study-related medical records. Study-related records identifying the subject will be kept confidential and, to the extent permitted by applicable laws and/or regulations will not be made publicly available. If any results of the study are published, the subject's identity will remain confidential.

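### Does the lack of a written procedure for masking the images leave the readers' blinding unprotected?

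*Combined protocol and SAP*

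**What the plan says.** The Blinding section opens with "This will be a semi-blinded trial" and then sets the rule: "Investigators performing the surgery will know whether or not a sponge is present but the investigators reviewing the images will not". Study Design adds that the readers are three spine surgeons, fellows of the centre, "who did not participate in the surgery will assess the images for the presence or absence of a retained surgical sponge", and that they do so postoperatively. The second Methods section, under the steps for all subjects, places the images on the hospital's "medical record system. Three investigators (TCSC Fellows, TBD) not participating in the surgery will independently view the images".

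Two records made before the reading may show the group. Under Randomization, "an envelope will be opened and the surgery worksheet annotated, as appropriate". In the second Methods section, the group 1 steps end the placement and removal of the sponge with the statement that "the circulating nurse will note this in your chart". The group 2 steps have no matching entry. They begin with "Two radiographs will be taken of the spine (AP and Lateral views) to verify that the instrumentation is placed properly" and finish with a sponge re-count.

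The Confidentiality section says "Data will be stored on TCSC computers, which are linked by Allina Health servers" and covers access by regulators and the IRB. It does not deal with masking of readers.

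**The concern.** Allocation is the reference standard in this study, and the reader's call is the test under evaluation. A reader who knows the group knows the right answer. All the accuracy measures in Statistical Methods rest on these calls, as does the comparison of one view with two. Calls made with knowledge of the group cannot be repaired afterwards, and a larger sample does not dilute the bias.

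Against that background, three features look uncomfortable together: a chart entry that exists for one group only, images held on the medical record system, and readers who belong to the same centre. The plan states that readers are blind but does not say how the images reach them. Coding or shuffling images is inexpensive, so its absence from the text looks like an oversight with consequences for the main result.

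**Working it through.** The plan gives no figure on this point, so the check is mainly a comparison of the text, followed by a look at whether a size can be attached.

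**1. What a leak would need, and what the text supports**

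| Step needed for a leak | What the documents say |
|---|---|
| A record of the group exists in the chart | Supported: removal is noted for group 1 only |
| The worksheet shows the group | Likely, not certain: it is annotated as appropriate, with no statement of what is written or whether both groups are marked |
| Readers have access to the worksheet | Not stated |
| Chart notes are seen when images are viewed | Not stated |
| Readers look at either record before making a call | Not stated, and contrary to the Blinding section |

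The first step is established and the second is probable. The rest are conjecture, and the last would breach the plan.

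**2. Effect on sensitivity if a leak occurred**

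Let Se be the true sensitivity and f the share of sponge-present reads in which the group is known and the call is then correct. Apparent sensitivity = Se + f(1 − Se). The 90% is the hypothesis in Sample Size. The 80% and all values of f are assumptions.

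| f | Se = 90% | Se = 80% |
|---|---|---|
| 0 | 90% | 80% |
| 5% | 90.5% | 81% |
| 10% | 91% | 82% |
| 20% | 92% | 84% |
| 50% | 95% | 90% |

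The same algebra applies to specificity. For scale, with 73 sponge cases (Randomization) the 95% half-width for one reader at 90% is 1.96 × √(0.9 × 0.1 / 73) = 0.069, or 6.9 points. The shifts in the 90% column are smaller than that. In the 80% column the shift reaches 10 points at f = 50%. Nothing in the documents limits f, so the table gives no upper bound on bias. It shows only the effect for each assumed f, and f = 0 if the Blinding section is followed.

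**3. Effect on one view versus two views**

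Suppose AP alone has 80% sensitivity, AP and LAT together have 90%, and f = 20%. All three are assumed for this illustration.

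- If informed readers mark the sponge on both views, AP alone becomes 80 + 0.2 × 20 = 84% and the pair becomes 90 + 0.2 × 10 = 92%. The difference falls from 10 to 8 points.
- If informed readers search harder and find on LAT only those sponges otherwise missed on both views, AP alone stays at 80% and the pair becomes 92%. The difference rises from 10 to 12 points.

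Readers record visibility on each view, so either pattern is possible. The direction is not established, and a loss of power for the McNemar test cannot be claimed.

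**The case for a change.** The strongest argument for a change is that the Blinding section states an aim without the means. Not taking part in the surgery, and reading independently of the other readers, do not control what appears on a reader's screen. A group-1-only chart entry gives the answer to anyone who sees it, the harm could not be reversed, and coding 146 image pairs would take only modest staff time. If the team intends to do this anyway, a sentence would make the blinding verifiable.

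Part of this stands. The documents do not describe how the images are presented, the chart entry does differ between groups, and any leak would tend to raise sensitivity and specificity. A reader of the eventual report would want to know how the images were shown.

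The step from there to a defect in the plan does not stand. The commitment that readers will not know sponge status is binding, and consulting the chart or worksheet to learn the group would depart from it. It is therefore wrong to say that nothing prevents unblinding. How much of the mechanics a short single-centre protocol should spell out is largely a matter of style. A written rule on coded images would not close every route either, since fellows of the centre might open a study patient's chart for reasons unrelated to the reading.

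**Conclusion.** The omission is real but is one of operational detail, and no change to the plan is called for. Carried out as written, with readers who were not in the operation, who read independently and who do not know whether a sponge was present, the study yields blinded calls and sound accuracy estimates. Preparing a masked image set is an ordinary way to carry out that rule and needs no amendment.

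No size can be attached from the documents. Under full compliance the bias is zero. Otherwise it depends on an assumed share of informed reads, and for the two-view comparison even the sign is open. The conclusion assumes that the team honours the Blinding section when it arranges the reading. It would not hold if readers were shown the images alongside the operative record, which no section describes.
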